**Cautionary Criteria:**

- Has any of the following conditions:
  - Autoimmune Disease
  - Diabetic
  - Herpes Simplex

Be sure to list all concomitant medications taken or procedures performed before, during and after the trial

Subjects will be recruited for the study through the existing patient database and may also be recruited through advertisements.

Subject populations will not be eligible to participate in the study if they are vulnerable populations such as children, pregnant women, prisoners, institutionalized individuals, and any persons requiring a legally authorized representative as part of the consenting process.

Subject population characteristics that will not be eligible to participate in the study include non-English speaking individuals and people who cannot read or comprehend English. Employees of the Investigator will be participating in the study.

#### **2.4 Screening**

Subjects will be asked questions about their medical history, may have a limited physical and their inclusion/exclusion criteria will be verified. Discontinuation of any concomitant medications will be discussed, and pretreatment instructions and post treatment instruction will be reviewed with the subject.

Procedure for the Limited Physical Exam:

If the investigator determines that a limited exam is necessary, the exam will be like a basic annual physical exam performed by a primary care doctor to determine general overall health. The limited medical exam may include all or any of the following; vital signs such as blood pressure, heart rate, respiratory rate and body temperature, general appearance, listening to the heart, lungs and abdomen with a stethoscope, head and neck exam, in addition to examining the throat, tonsils, teeth, ears, eyes and nose as well as a neurological exam such as testing muscle strength, reflexes, balance, sensory changes of the extremities and mental state.

#### **2.5 Informed Consent Process and Enrollment**

Subjects will be asked to review the pre and post treatment instructions prior to signing the informed consent form and their involvement in the study. Subjects will be informed of site's COVID-19 procedures that adhere to federal and state guidelines at this time. Subjects who sign the informed consent will be screened to confirm eligibility and, if eligible, will be assigned a subject identification number. Subjects will be de-identified through their subject identification number, which will be stored in a secure location. Subject identification numbers will be generated chronologically and assigned only to subjects who have met all the study selection criteria and have signed the informed consent form. The informed consent will be obtained prior to a subject's involvement in any study related procedures. A subject will be considered enrolled in the study once they have signed the informed consent form.

The following Pre-Treatment instructions will be reviewed:

- Shave any visible hair on the area to be treated.
- Do not wear constrictive clothing. Your abdomen or flanks must be accessible for the neutral pad to be attached.
- Remove all makeup and lotions from the treatment area and all jewelry and metal objects from the body.
- For an optimum treatment, keep hydrated by drinking water (at least 8 cups daily) or hydrating fluids, such as Gatorade, and avoid drinking alcohol for 24 hours in advance.

The following post treatment instructions will be reviewed:

- If the skin is slightly pink or red in areas following the treatment, avoid hot water when washing or showering until any erythema (redness) has subsided.
- Soothing creams or moisturizers, such as Aveeno, may be used.
- Gently massage the treated area daily for 5 minutes for the duration of your involvement in the study.
- Use a sun block with UVA and UVB protection with SPF of 30 or greater to prevent sun damage.
- Maintain the same weight and exercise routine throughout the study.

## **2.6 Pre-Treatment Procedures**

If the subject is of childbearing potential (i.e. females not post-menopausal or not surgically sterile), pregnancy verification will be required. Pregnancy verification will be performed by asking the subject if they are pregnant, the date of their last menstrual cycle, and be required to perform a urine pregnancy test at the site. For Group A, pregnancy verification will be performed prior to the subject's first treatment and prior to their 5th treatment. Pregnancy verification will be performed by verifying the date of their last menstrual cycle at each subsequent treatment. For Group B, pregnancy verification will be performed prior to the subject's first treatment and prior to each treatment only if their treatment is 30 days past their last pregnancy verification. A urine pregnancy test may also be conducted at the Investigator/clinician's discretion at any time during the study. If a urine pregnancy test is conducted, then a negative result must be obtained within 24 hours prior to the treatment.

### Urine Pregnancy Test Procedure:

1. A urine sample is tested mid-stream or by cup sample with an indicator stick.
2. Negative results are indicated on the indicator stick.

#### Group A:

- Photographs will be taken prior to the 1st and 5th treatment, and may be taken prior to each subsequent treatment.
- Prior to treatment 1 and 5 only, circumference measurements and abdomen strength measurement will be taken, and ultrasounds may be performed.
- Prior to treatment 5 only, subjects will be asked to complete a Subject Treatment Questionnaire.
- For treatment 5 only, pre-treatment procedures and treatment may be separated into 2 visits.

#### Group B:

- Photographs will be taken prior to their first treatment and may be taken prior to each subsequent treatment.
- Circumference measurements and abdomen strength measurements may be taken, and ultrasounds may be performed at any treatment visit.
- Subjects may be asked to complete a Subject Treatment Questionnaire prior to any treatment visit.

## **2.7 Treatment Procedures**

- The defined study area will be identified and may be marked with a surgical marker.

- Procedures for the Brera/Med 400 treatment:
  - The applicators will be placed in contact with the skin.
  - The entire defined treatment area will then be treated by delivering energy to the skin.
  - Temperature may be continuously monitored and recorded during treatment.
- Parameters may be adjusted throughout the treatment to increase subject comfort.
- Subjects will be asked to report the general level of treatment discomfort/pain on a scale of 0 (none) to 10 (maximum intolerable pain).
- Photographs may be taken during treatment.
- The additional treatments will follow the same procedure.

### **2.8 Post Treatment Procedures**

- Adverse events will be documented after treatment.
- Photographs may be taken post treatment.
- Post treatment instructions will be reviewed with the subject.

### **2.8 Follow Up**

#### Group A:

- Subjects may receive a phone call 1 week (1-7 days) after each treatment to record side effects.
- Subjects will return for follow up visits at 30 and 90 days post last treatment.
- Photographs will be taken, adverse events will be documented, and subjects will be asked to complete questionnaires, objective measurements will be taken, and ultrasounds may be performed.
- Any subject affected by COVID-19 that is not able to attend their follow up visits to complete the study will be asked to return to the site for a final follow up visit within 1 year of last treatment.

#### Group B:

- Subjects may receive a phone call 1 week (1-7 days) after each treatment to record side effects.
- Subjects may return for follow up visits at 30 and 90 days post last treatment.
- Photographs will be taken, adverse events will be documented, and subjects may be asked to complete questionnaires and objective measurements may be taken and ultrasounds may be performed.

Some subjects may have an incomplete response or no response by the end of the study. At the end of the study, treatments using an FDA approved/cleared treatment method may be discussed with the subject and obtained at the cost of the subject.

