## 2.0 PROTOCOL

### **2.1 Protocol Methodology and Analysis**

Methodology:

Subjects are to be enrolled in this clinical study if they are a healthy male or female 18 years of age or older. Up to 30 subjects will be enrolled at 1 study center. Subjects will be enrolled into 2

groups, Group A and Group B. Subjects will be enrolled in Group A if they present with abdominal fat and are able to be present for all visits as outlined in “Schedule of Visits and Procedures – Group A”. Subjects will enroll in Group B for training and experience purposes only and will follow the visit schedule as outlined in “Schedule of Visits and Procedures – Group B”. Randomization will not be required as each subject will be assigned to a group depending on the purpose of their treatment(s). All subjects will attend a screening/pretreatment visit which may be performed on the same day as the treatment visit.

Subjects in Group A will receive up to 8 treatments with the Brera/Med 400 device on their abdomen or flanks. Subjects may receive a phone call 1 week (1-7 days) after each treatment to record side effects. Subjects will return for follow up visits at 30 and 90 days post last treatment for efficacy and side effects assessments.

Subjects in Group B may receive up to 8 treatments with the Brera/Med 400 device on their abdomen and/or flanks. Subjects may receive a phone call 1 week (1-7 days) after each treatment to record side effects. Subjects may be asked return for follow up visits at 30 and 90 days post last treatment for efficacy and side effects assessments.

An unscheduled visit or phone call may be performed at any time during the study at the request of the subject or as deemed necessary by the site Investigator.

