**Group B:**

	Visit #1*	Visit #2-9	Call (optional)	Visit #10 (optional)	Visit #11 (optional)
Procedure	Screening and Pretreatment Procedures	Treatment Visit(s) 1-8 (At least 3 days apart)	Phone Call 1 Week Post Tx (1-7 Days)	Follow Up 30 Days Post Last Tx (± 10 Days)	Follow Up 90 Days Post Last Tx (± 10 Days)
Medical History	X				
Weight/BMI	X	X		X	X
Pregnancy Verification	X	X***			
Informed Consent	X				
Photographs (2D)	X	X**		X	X
Photographs (3D)**	X	X		X	X
Ultrasounds**	X	X		X	X
Circumference Measurement **	X	X		X	X
Abdomen Strength Measurement**	X	X		X	X
Treatment		X			
Treatment Discomfort/ Pain Evaluation		X			
Subject Treatment Questionnaire**		X		X	X
Subject Satisfaction**				X	X
SGAIS**				X	X
PGAIS**				X	X
Adverse Events Assessment	X	X	X	X	X

\*Screening and Pretreatment Procedures may occur at the same time as the first Treatment Visit.

\*\*Optional.

\*\*\*Pregnancy verification only required prior to each treatment if their treatment is 30 days past their last pregnancy verification.

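### Group B has no required adverse event contact after its last treatment day but counts in the by-group safety percentages, so its percentage for later-starting events may be too low

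*Combined protocol and SAP*

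**What the plan says.** Section 2.1 gives the purpose of the second group: "Subjects will enroll in Group B for training and experience purposes only". Its members may have up to 8 treatments, with no stated minimum, and for later contact "Subjects may be asked return for follow up visits at 30 and 90 days post last treatment".

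Section 2.8 (Follow Up; 2.9 in the table of contents) repeats this for Group B: "Subjects may return for follow up visits at 30 and 90 days post last treatment". The call is worded the same way: "Subjects may receive a phone call 1 week (1-7 days) after each treatment to record side effects". The Group B schedule in 2.12 marks the call, visit 10 and visit 11 as optional. The required adverse event assessments are at screening and at treatment visits, and section 2.8 (Post Treatment Procedures) states "Adverse events will be documented after treatment". Under the Group B schedule, "Screening and Pretreatment Procedures may occur at the same time as the first Treatment Visit".

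For Group A, section 2.8 says "Subjects will return for follow up visits at 30 and 90 days post last treatment", and the schedule sets a window of 10 days either side. Group A's 1-week call is optional as well.

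Section 2.15.3 defines the safety set as subjects treated at least once who have some safety data. Section 2.15.6 summarises adverse events by treatment group as number and percent, without statistical comparison. Section 1.2 makes adverse events the primary objective. Section 2.15.1 makes success depend on the physician finding the side effect profile acceptable.

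**The concern.** A Group B subject who finishes treatment and is never contacted again still enters the Group B denominator. In a number-and-percent table, that subject looks the same as one who was asked at 30 and 90 days and had no event. If some subjects are not contacted and do not report on their own, events starting after the last treatment are missed while the denominator stays whole, and the percentage falls below the truth.

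The affected summary serves the primary objective and feeds the physician's judgement of acceptability. Section 3.3 describes the device as uncleared with limited safety data, so a reader may give weight to a low percentage that partly reflects nobody having asked.

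**Working it through.** The plan gives no figure for this point, so there is nothing to reproduce. The check compares required contact in the two groups and then illustrates the possible effect.

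**Required adverse event contact after the last treatment (2.8, 2.12)**

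| Contact | Group A | Group B |
|---|---|---|
| Last treatment day | required | required |
| 1-week call (days 1-7) | optional | optional |
| Visit 10 (30 ± 10 = days 20-40) | required | optional |
| Visit 11 (90 ± 10 = days 80-100) | required | optional |

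Required observation after the last treatment therefore runs to day 80-100 in Group A and is 0 days in Group B.

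**Time on treatment in Group B.** With one treatment and same-day screening, all required contact falls on one day. With 8 treatments at the minimum 3-day spacing, first to last treatment spans 7 × 3 = 21 days. Events arising between treatments can be picked up at the next treatment visit. In either case, 0 required days follow the last treatment.

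**Do other provisions close the gap?**
- The adverse event wording for Group B follow-up in 2.8 applies only if the subject returns.
- The follow-until-resolved rules in 2.14 and 14.0 concern events already known.
- Section 14.0 says events are captured throughout the study, but this creates no contact.
- Subject-initiated contact (14.0) and unscheduled visits (2.10) depend on the subject or on the investigator's discretion.
- The final visit in 12.0 is for subjects who withdraw.
- The inclusion criterion in 2.3 on being able to attend all visits does not make an optional visit required.

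None of these requires contact with a subject who simply completes treatment.

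**Illustration.** Let c be the share of subjects contacted after the last treatment and s the chance that an uncontacted subject self-reports. Assume that contact is unrelated to having an event and that it reveals any event. For events starting after the last treatment day:

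reported / true = c + (1 − c) × s

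| c | s | Ratio | Reported when truth is 10% |
|---|---|---|---|
| 1 | any | 1.00 | 10% |
| 0.5 | 0.5 | 0.5 + 0.5 × 0.5 = 0.75 | 7.5% |
| 0.5 | 0 | 0.50 | 5% |
| 0 | 0 | 0 | 0% |

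The 10%, c and s are all assumptions. At a ratio of 0.50, a true 5% would show as 2.5% and a true 20% as 10%.

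With an assumed 10 Group B subjects and a true 10%, the chance of recording at least one late event is 1 − (1 − 0.10 × k)^10, where k is the share of late events captured. This gives 65% at k = 1, 40% at k = 0.5 and 22% at k = 0.25.

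**Would requiring the 1-week call be enough?** A call made anywhere in days 1-7 would satisfy it. Against Group A's day 80-100, it leaves between 80 − 7 = 73 and 100 − 1 = 99 days without a required question. A call in the 30-day window (days 20-40) reduces this to between 80 − 40 = 40 and 100 − 20 = 80 days.

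**The case against.** The lighter schedule is deliberate and its reason is stated. Group A supplies the required 30 and 90 day safety data, the safety summary is by group and untested, and the success criterion has no numerical threshold. All of this stands, and it limits how much depends on Group B. It does not justify counting subjects who were never asked as free of later events.

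The bias is also conditional. The documents give no onset times. Of the anticipated effects in 2.14, prolonged swelling and redness describe persistence, and late onset of others, such as infection or nodules, is assumed. Subjects with a problem may be more likely to be seen, because the site may ask them back or they may request a visit; this would make the shortfall smaller than the formula shows. Chance variation is large as well. With an assumed 5 to 15 subjects, one subject is 1/15 = 6.7 to 1/5 = 20 percentage points. At n = 10, the standard error of a true 10% is √(0.1 × 0.9 / 10) = 9.5 points, more than the illustrated shifts of 2.5 and 5 points. These arguments stand as limits on size. Even so, the shift runs in one direction and the planned table does not reveal it.

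Contact dates should be recoverable from the study records, so the number assessed could be counted afterwards, and 2.15.6 does not forbid this. That is fair, but 2.15.6 does not ask for it either.

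A reader might infer that the study's overall safety result is biased, or that a comparison of the two groups is invalidated. The documents do not support either reading: no pooled percentage and no between-group safety test is planned.

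**Conclusion.** The point holds in a limited form. Group B has no required adverse event contact after the last treatment day, and its treated subjects enter the by-group percentages with no minimum follow-up. The Group B percentage for events starting after the last treatment may therefore be too low.

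The difference in required observation, day 80-100 against day 0, follows directly from the schedules. The size of any understatement cannot be calculated, because contact uptake, self-reporting, late-event rates and the size of Group B are not given. There is none if all subjects are contacted in time or report for themselves. The conclusion takes treatment group in 2.15.6 to mean Groups A and B, the only groups in the protocol.

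The consequence is confined to the descriptive Group B summary, one input to the physician's judgement. Priority is low to moderate.

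**What to change.** 1. **Section 2.15.6.** For each group, report the number of subjects actually assessed for adverse events at each time point after the last treatment: 1-week call, 30 days and 90 days. Show later-onset events against that number, alongside the all-treated denominator. The assessed-only percentage is unbiased only if being assessed is unrelated to having an event, so both should be shown. A single count of subjects with any later contact is not enough, because it would treat a day-1 call like a day-90 visit.

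2. **Sections 2.1, 2.8 (Follow Up) and 2.12.** For Group B subjects who do not attend visit 10, require at least one adverse event phone contact after the last treatment, in the existing 30 ± 10 day window. The 1-week call alone would leave later events unasked. If the 1-week call after the last treatment is also made required, do so in both groups, since it is optional in Group A too.

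This does not bring Group B to day 90; the counts in item 1 make the remaining gap visible.

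**Cost.** For an assumed 5 to 15 Group B subjects, item 2 needs at most 5 to 15 short calls. Requiring the 1-week call in both groups adds one call per subject, 20 to 30 on the totals in 2.15.2 and 2.1, for at most 20 + 5 = 25 to 30 + 15 = 45 calls. The change also needs a protocol amendment with written IRB approval (section 21.0) and one extra table row per time point. Group A visits do not change.

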**2.10 Unscheduled Visits**

An unscheduled visit may be performed at any time during the study at the subject's request or as deemed necessary by the site Investigator. The date and reason for the unscheduled visit will be recorded in the source documentation.

**2.11 Replacement of Subjects**

Replacement of subjects who have withdrawn or been withdrawn from the study will be allowed to be replaced with prior approval from the sponsor and/or IRB.

**2.12 Schedule of Visits and Procedures****Group A:**

	Visit #1*	Visit #2-9	Call (optional)	Visit #10	Visit #11
Procedure	Screening and Pretreatment Procedures	Treatment Visit(s) 1-8 (1 Week Apart $\pm$ 4 Days)	Phone Call 1 Week Post Tx (1-7 Days)	Follow Up 30 Days Post Last Tx ( $\pm$ 10 Days)	Follow Up 90 Days Post Last Tx ( $\pm$ 10 Days)
Medical History	X				
Weight/BMI	X	X**		X	X
Pregnancy Verification	X	X**			
Informed Consent	X				
Photographs (2D)	X	X		X	X
Photographs (3D)	X	X**		X	X
Ultrasounds	X	X**		X	X
Circumference Measurement	X	X**		X	X
Abdomen Strength Measurement***	X	X**		X	X
Treatment		X			
Treatment Discomfort/ Pain Evaluation		X			
Subject Treatment Questionnaire		X**		X	X
Subject Satisfaction				X	X
SGAIS				X	X
PGAIS				X	X
Adverse Events Assessment	X	X	X	X	X

\*Screening and Pretreatment Procedures may occur at the same time as the first Treatment Visit.

\*\*Performed pre-treatment 5, optional at other treatment visits.

\*\*\*Optional

**Group B:**

	Visit #1*	Visit #2-9	Call (optional)	Visit #10 (optional)	Visit #11 (optional)
Procedure	Screening and Pretreatment Procedures	Treatment Visit(s) 1-8 (At least 3 days apart)	Phone Call 1 Week Post Tx (1-7 Days)	Follow Up 30 Days Post Last Tx (± 10 Days)	Follow Up 90 Days Post Last Tx (± 10 Days)
Medical History	X				
Weight/BMI	X	X		X	X
Pregnancy Verification	X	X***			
Informed Consent	X				
Photographs (2D)	X	X**		X	X
Photographs (3D)**	X	X		X	X
Ultrasounds**	X	X		X	X
Circumference Measurement **	X	X		X	X
Abdomen Strength Measurement**	X	X		X	X
Treatment		X			
Treatment Discomfort/ Pain Evaluation		X			
Subject Treatment Questionnaire**		X		X	X
Subject Satisfaction**				X	X
SGAIS**				X	X
PGAIS**				X	X
Adverse Events Assessment	X	X	X	X	X

\*Screening and Pretreatment Procedures may occur at the same time as the first Treatment Visit.

\*\*Optional.

\*\*\*Pregnancy verification only required prior to each treatment if their treatment is 30 days past their last pregnancy verification.

### **2.13 Evaluation Methods**

#### **Photographs:**

Photographs 2D and 3D will be taken at baseline, pre-treatment 5 and at the 30 and 90 day follow up visit, and may be taken at each additional treatment visit to assess the efficacy and safety of treatment. 2D photography may be taken at any time during treatment to document treatment performance and/or adverse events.

**Treatment Discomfort/Pain Evaluation:**

Subjects will be asked to report the general level of treatment discomfort on a scale of 0 (none) to 10 (maximum intolerable pain) using the universal pain assessment tool (Appendix B)

**Subject Treatment Questionnaire:**

Subject treatment questionnaires may be collected from each subject to obtain feedback on their treatment experience.

**Blinded Evaluation:**

Three blinded independent reviewers will perform a photographic evaluation in which they will be asked to identify pre-treatment images when compared to post treatment images. The reviewers will be Board Certified Dermatologists and/or Surgeons and will be chosen based on availability and have relevant clinical experience. They will attend a training session prior to grading.

